Appendix 7. Perception of Treatment Assignment Questionnaire

In which arm of the study do you think you have been participating?

- Active arm (GS-6615)
- Placebo arm (sugar pill)

Appendix 8. Pregnancy Precautions, Definition for Female of Childbearing Potential, and Contraceptive Requirements

1) Pregnancy and Contraception Requirements for Males and Females of Childbearing Potential

The risks of treatment with GS-6615 during pregnancy have not been evaluated. Pregnancy must be excluded before the start of treatment with study drug and prevented thereafter by reliable contraceptive methods. Pregnancy tests will be performed regularly throughout this study. Please refer to the latest version of the investigator's brochure for additional information.

2) Definition of Female of Childbearing Potential

For the purposes of this study, a female subject of childbearing potential is a nonmenopausal female who has not had a hysterectomy, bilateral oophorectomy, or medically documented ovarian failure. This definition includes a pubertal female who has not yet started menstruating and perimenopausal women who have had a spontaneous menses in the last 12 months. A woman who has had a tubal sterilization is considered to be of childbearing potential for pregnancy testing purposes.

A female subject may be considered menopausal in either of the following conditions:

- Surgical menopause: Appropriate medical documentation of prior complete bilateral oophorectomy (ie, surgical removal of the ovaries and occurring at the age at which the procedure was performed)
- Spontaneous menopause: Permanent cessation of previously occurring menses as a result of ovarian failure with documentation of hormonal deficiency by a certified health care provider. The worldwide mean age of spontaneous menopause is 49.24 (SD 1.73) years
- A hormonal deficiency should be properly documented in the case of suspected spontaneous menopause as follows:
 - If age ≥ 54 years and with the absence of normal menses: serum follicle stimulating hormone (FSH) level elevated to within the postmenopausal range based on the laboratory reference range where the hormonal assay is performed
 - If age < 54 years and with the absence of normal menses: negative serum or urine human chorionic gonadotropin (hCG) with concurrently elevated serum FSH level in the postmenopausal range, depressed estradiol (E2) level in the postmenopausal range, and absent serum progesterone level, based on the laboratory reference ranges where the hormonal assays are performed

3) Contraceptive Requirements

Male subjects and female subjects of childbearing potential who engage in intercourse must agree to utilize protocol specified methods of contraception from the screening visit throughout the study period and for 90 days following the last dose of study drug. Female study subjects

who are not heterosexually active must provide periodic confirmation of continued abstinence from heterosexual intercourse and regular pregnancy testing while taking study drug. The investigator will counsel subjects on the protocol specified method(s) for avoiding pregnancy in case the subject chooses to engage in heterosexual intercourse.

Protocol specified contraceptive methods are as follows: (1) a combination of one hormonal method and one barrier method; (2) two barrier methods where one method is the male condom; or (3) use of an intrauterine device (IUD) or tubal sterilization; see [Appendix Table 1](#) below. Acceptable hormonal methods include injectable progesterone, progesterone implants, combination oral contraceptives, transdermal contraceptive patch, and vaginal ring. Acceptable barrier methods include diaphragm with spermicide, cervical cap with spermicide, and the male condom. Female subjects must use either a hormonal method or a barrier method if the partner has a vasectomy. If a subject has undergone tubal sterilization or has had a Copper T 380A IUD or LNg 20 IUD inserted, no other contraception is needed.

If tubal sterilization is via the Essure procedure, verification of tubal blockage by hysterosalpingogram (HSP) must be performed approximately 3 months after microinsertion. Prior to verification, Essure is not considered a reliable form of contraception and the contraception methods described below must be used.

Female subjects who utilize hormonal contraceptives as one of their birth control methods must have used the same method for at least 3 months before study dosing (Randomization).

Female subjects of childbearing potential must have a negative serum pregnancy test at Screening and a negative urine pregnancy test at Randomization (Day 1) prior to receiving the first dose of study drug. Lactating females must discontinue nursing before study drug administration.

Appendix Table 1. Protocol Specified Contraceptive Methods

Methods to Use by Themselves	Combination Methods	
	Hormone Methods (choose one and use with a barrier method)	Barrier Methods (use both OR choose one and use with a hormone method)
Intrauterine Devices (IUDs) - Copper T 380A IUD - LNg 20 IUD Tubal Sterilization	Estrogen and Progesterone - Oral contraceptives - Transdermal patch - Vaginal ring Progesterone - Injection - Implant	- Diaphragm with spermicide OR - Cervical cap with spermicide - Male condom (with or without spermicide)
Partner's vasectomy must be used with a hormone or barrier method.		

The investigator will counsel all subjects on the most effective method(s) for avoiding pregnancy during the study.

4) Additional Requirements for Male Subjects

Male subjects must agree to use condoms during heterosexual intercourse and avoid sperm donation while enrolled in the study and for at least 90 days after administration of the last dose of study drug.

Use of condoms, with or without spermicide, has been proven to decrease the risk of transmission of HIV and other sexually transmitted diseases. The use of spermicide is not recommended if the subject or subject's partner is infected with HIV.

5) Procedures to be Followed in the Event of Pregnancy

Subjects will be instructed to notify the investigator if they become pregnant at any time during the study, or if they become pregnant within 90 days of last study drug dose. Subjects who become pregnant or who suspect that they are pregnant during the study must report the information to the investigator and discontinue study drug immediately. Male subjects whose female partner has become pregnant or suspects she is pregnant during the study and within 90 days of the last study drug dose of the male subject must report the information to the investigator.

Instructions for reporting pregnancy, partner pregnancy, and pregnancy outcome are outlined in Section [7.5.2.1](#).

Appendix 9. Classification of Strong Inhibitors and Inducers of CYP3A

Strong CYP 3A Inhibitors^a		
Drug	Half-life	Time to 5 half-lives
Clarithromycin	3 - 4 hours	15 – 20 hours
Indinavir	1.8 (± 0.4) hours	9 hours
Itraconazole	21 hours	105 hours
Ketoconazole	Plasma elimination is biphasic with a half-life of 2h during the first 10h, and a half-life of 8h after 10h	10 – 40 hours
Nefazodone	2 - 4 hours	10 – 20 hours
Nelfinavir	3.5 - 5 hours	17.5 – 25 hours
Ritonavir	3 - 5 hours	15 – 25 hours
Saquinavir	9 - 15 hours	45 – 75 hours
Telithromycin	10 hours	50 hours

a Please note the following: A strong inhibitor is one that caused a ≥ 5 -fold increase in the plasma AUC values or more than 80% decrease in clearance

Strong CYP 3A Inducers		
Drug	Half-life	Time to 5 half-lives
Carbamazepine	36 hours (single dose), 16-24 hours (repeated dosing)	180 hours (single dose), 80-120 hours (repeated dosing)
Efavirenz	40 - 55 hours	200 – 275 hours
Modafinil	15 hours	75 hours
Nevirapine	45 hours	225 hours
Oxcarbazepine	1 - 5 hours (healthy adults)	5 – 25 hours
Phenobarbital	53 - 118 hours	265 – 590 hours
Phenytoin	6 - 24 hours	30 – 120 hours
Rifabutin	28 - 62 hours	140 – 310 hours
Rifampin	1.5 - 5 hours	7.5 – 25 hours

MMRM	mixed models repeated measurement
NYHA	New York Heart Association
OLE	open-label extension
PE	physical examination
PK	pharmacokinetics
PP	per protocol
PR	electrocardiographic interval occurring between the onset of the P wave and the QRS complex representing time for atrial and ventricular depolarization, respectively

[figure not shown]
PT	preferred term
Q1	first quartile
Q3	third quartile
QRS	electrocardiographic deflection between the beginning of the Q wave and termination of the S wave representing time for ventricular depolarization
QT	electrocardiographic interval between the beginning of the Q wave and termination of the T wave representing the time for both ventricular depolarization and repolarization to occur
QTc	corrected QT
QTcB	corrected QT (Bazett's formula)
RR	electrocardiographic interval representing the time measurement between the R wave of one heartbeat and the R wave of the preceding heartbeat
SAE	serious adverse event
SAP	statistical analysis plan
SMQ	Standardized MedDRA queries
SOC	system organ class
WHO	World Health Organization

1. INTRODUCTION

This statistical analysis plan (SAP) describes the statistical methods to be used during the final reporting and analysis of data collected under Gilead Sciences, Inc. Protocol GS-US-361-1157 “A Phase 2/3, Randomized, Double-Blind, Placebo-Controlled Study to Evaluate the Effect of GS-6615 on Exercise Capacity in Subjects with Symptomatic Hypertrophic Cardiomyopathy.”

This SAP was updated to reflect a synoptic CSR. All planned listings will be produced, however summaries will only be provided for primary and secondary endpoints, relevant exploratory endpoints, and relevant safety measures.

1.1. Study Objectives

Primary Study Objective	
• Evaluate the effect of eleclazine on exercise capacity, as measured by Peak VO₂ achieved during cardiopulmonary exercise testing (CPET), in subjects with symptomatic hypertrophic cardiomyopathy (HCM)
Secondary Study Objectives	
• Evaluate the safety and tolerability of eleclazine in subjects with symptomatic HCM• Evaluate the effect of eleclazine on quality of life as measured by the Minnesota Living with Heart Failure Questionnaire (MLHFQ)• Evaluate the effect of eleclazine on treadmill exercise time during CPET
Exploratory Objectives	
PPD
  The Exploratory Objectives section contains four redacted entries, each marked with a small blue square icon on the left. The text of these entries is completely obscured by blue bars.

1.2. Study Design

Design Configuration and Subject Population	
This is a randomized, double-blind, placebo-controlled, global, multicenter study to evaluate the effect of eleclazine on exercise capacity in subjects with symptomatic HCM.
 
Eligible subjects will be enrolled and randomized 1:1 to receive either eleclazine or matching placebo for a minimum treatment duration of 24 weeks. Randomization will be stratified by sex and by age (≥ 50 years and < 50 years).

Treatment Groups	
Eleclazine
 
Day 1 through End of Double-Blind Treatment (EDBT)
 
Oral single loading dose of 30 mg eleclazine (5×6 mg tablets) on Day 1, followed by maintenance dose of 3 mg eleclazine (1×3 mg eleclazine tablets) once daily until Week 12 then daily maintenance dose of 6 mg (2×3 mg eleclazine tablets) from Week 12 to at least Week 24 visit
 
Day of EDBT
 
Oral single, double-blind loading dose of placebo (5 tablets) on day of EDBT visit (to maintain retrospective blinding to double-blind study treatment assignment).
 
Placebo
 
Day 1 through EDBT
 
Oral single loading dose of placebo to match eleclazine ($5 \times$ placebo tablets) on Day 1, followed by daily maintenance dose of matching placebo ($1 \times$ placebo tablet) until Week 12 then daily maintenance dose of matching placebo ($2 \times$ placebo tablets) from Week 12 to at least Week 24 visit
 
Day of EDBT
 
Oral single, double-blind loading dose of eleclazine (5×6 mg tablets) on day of EDBT visit (to maintain retrospective blinding to double-blind study treatment assignment).
 
Open-label Extension (OLE) Period
 
Maintenance dose of 6 mg open-label eleclazine (2×3 mg eleclazine tablets) once daily through the end of the open-label extension period

Key Eligibility Criteria	
Subjects with symptoms (New York Heart Association [NYHA] Class \geq II dyspnea or Canadian Cardiovascular Society [CCS] Class \geq II angina) due to HCM (defined as a maximal LV wall thickness of \geq 15 mm in the absence of other causative loading abnormalities capable of producing the magnitude of hypertrophy observed) will be randomized.
 
Subjects with and without left ventricular outflow tract obstruction will be eligible.
 
Medications commonly used in the treatment of HCM are permitted, unless specifically excluded, and may be continued throughout the study, including beta-blockers, calcium channel blockers, and Class III antiarrhythmics (eg, amiodarone and sotalol). It is recommended that the doses of such medications remain stable after screening through the end of the double-blind treatment period, unless clinically warranted at the discretion of the investigator.
 
Inclusion Criteria
 
Subjects must meet all of the following inclusion criteria to be eligible for participation in this study.
 
1) Have the ability to understand and sign a written informed consent form, which must be obtained prior to initiation of study procedures2) Males and females 18 to 65 years old, inclusive3) Established diagnosis of HCM defined by standard criteria as a maximal LV wall thickness \geq 15 mm at initial diagnosis in the absence of other causative loading abnormalities capable of producing the magnitude of hypertrophy observed4) Exertional symptoms including at least one of the following:
a) NYHA Class \geq II Dyspneab) CCS Class \geq II Angina5) Screening (baseline) Peak $VO_2 < 80\%$ of predicted based on age, sex, and weight-adjusted equations (see Appendix 4 of the protocol), as confirmed by the investigator6) Ability to perform an upright treadmill CPET
---------------------------------	---

	
7) Hemodynamically stable at both Screening and Randomization visits defined as: systolic blood pressure ≥ 90mmHg, heart rate ≤ 100 beats/min, and not requiring mechanical circulatory support or intravenous treatment with diuretics or vasoactive drugs
 
8) Male subjects and female subjects of childbearing potential who engage in heterosexual intercourse must agree to utilize protocol-specified method(s) of contraception as described in Appendix 8 of the protocol.
 
See protocol for exclusion criteria.


Study Periods/Phases
	
Subjects will be seen in the clinic for a Screening visit (within 14 to 28 days prior to Randomization; within 14 to 60 days for those enrolled under Protocol Amendment 1), a Randomization visit, and during the treatment period at Week 2, 6, 12, 18, and 24 visits. Subjects will be contacted between study visits for assessment of adverse events and concomitant medications. In order to accumulate additional long-term safety data in this population, subjects will continue double-blind treatment (and 12-weekly assessments) until the last subject has been followed up for approximately 24 weeks. As that date approaches, all remaining subjects (including subjects who have already discontinued treatment but are continuing the study) will be contacted to return for the EDBT Period visit. At the end of the double-blind, placebo-controlled treatment period, all subjects who complete the treatment period (including study drug dosing) may continue in the study, at the discretion of the investigator, and receive eleclazine in an OLE. During the OLE period, subjects will continue to undergo periodic required assessments. A safety follow-up visit will occur 30 days after the last dose of study drug. The schedule of follow-up and OLE visits may vary according to country specific requirements.

Schedule of Assessments

The study includes 4 periods: Screening, Double-Blind Placebo-Controlled Treatment (minimum of 24 weeks), Open-Label Extension (OLE), and Follow-up (30 days after last dose). During the Screening phase, baseline CPET as well as implantable cardioverter-defibrillator (ICD) interrogation, where applicable, will be performed and subjects will wear the ZIO[®] XT Patch which will be collected on Day 1. Demographic, medical history, adverse events (AE), concomitant medications, physical examination (PE), ECG, ECHO, and vital signs results will be recorded and samples will be collected for laboratory results.

[figure not shown]
Eligible subjects will be randomized on Day 1. Pharmacokinetic (PK), NT-proBNP and hsTnT samples will be collected, and ECG, ECHO, MLHFQ, and PE including vitals will be performed. Study drug will be dispensed on Day 1 and all subsequent study visits during the double-blind placebo-controlled treatment and the OLE periods.

During the double-blind placebo-controlled period, subjects will be contacted on Weeks 1, 9, 15, and 21 to review AEs and concomitant medications and have visits on Weeks 2, 6, 12, 18, 24, and every 12 weeks after Week 24 through EDBT. During these visits, samples for PK and laboratory results, unused study drug and the ZIO[®] XT Patch will be collected and PE, including vitals, and ECG will be performed. Additionally, at the Week 12 and 24 visits, ECHO, CPET, MLHFQ, and samples for NT-proBNP and hsTnT will be collected and ICD interrogation, where applicable, will be performed.

During the OLE period, subject will be contacted at OLE Week 1 and have visits at OLE Weeks 12 and 24 and every 24 weeks thereafter and include PK (through OLE Week 24) and lab sample collection, PE including vitals, ECG, and returning and dispensing study drug.

The follow-up period consists of a visit 30 days after the last dose of study drug with the same assessments that were performed during the OLE period. The schedule of follow-up and OLE visits may vary according to country specific requirements.

A schematic of the study is presented below.

- * Subjects will continue double-blind treatment until the last subject has been followed up for approximately 24 weeks. As that date approaches, all remaining subjects (including subjects who have already discontinued treatment but who are continuing the study) will be contacted to return for the End of Double-Blind Treatment Period visit.
- ** Subjects who complete double-blind treatment period at a down-titrated dose of 1 tablet of blinded study drug once daily are eligible to continue into the open-label extension period. It is encouraged that these subjects attempt the target dose of eleclazine 6 mg once daily (2 x 3 mg eleclazine tablets), if appropriate in the opinion of the investigator.

See Appendix 1 for the complete study procedures table.

Randomization	
Eligible subjects will be randomized in a 1:1 ratio to one of the following groups:
 
 1) 30 mg single loading dose of eleclazine on Day 1 followed by 3 mg daily dose of eleclazine until Week 12 and 6 mg daily dose of eleclazine from Week 12 to at least Week 24 2) Matching placebo single loading dose on Day 1 followed by matching placebo until Week 12 and matching placebo from Week 12 to at least Week 24 
Randomization will be stratified by sex and by age (≥ 50 years and < 50 years). There will be up to 60 sites.

Site and/or Stratum Enrollment Limits	
There were no site enrollment limits.

Study Duration	
The enrollment period is expected to be 12 months. The maximum double-blind treatment period is approximately 20 months. The OLE period will be up to a maximum of approximately 32 months. The OLE period will continue until eleclazine is commercially available for the treatment of patients with HCM, or the investigator deems it no longer in the subject's best interest, or until Gilead terminates development of the study drug for the treatment of patients with HCM. The maximum length of participation in the OLE varies as applicable by local country requirements.

1.3. Sample Size and Power

Planned Sample Size	
The planned sample size is 180 (90 per arm).

Power Statement	
Based on a 2-sided, 2-sample t-test ($\alpha = 0.01$), and a standard deviation of 4 mL/kg/min, a sample size of 90 subjects per arm provides greater than 95% power assuming a treatment difference of 3 mL/kg/min in the primary endpoint (Peak VO_2) given a null hypothesis of no treatment effect. This treatment difference is clinically significant and similar to that seen with alcohol septal ablation {Firoozi 2002}. The program nQuery Advisor[®] version 6.0 (Statistical Solutions, Cork, Ireland) was used for sample size and power calculations.

2. TYPE OF PLANNED ANALYSIS

The Data Monitoring Committee (DMC) periodically reviewed safety data as specified in its charter.

This study was terminated by the Sponsor prior to the end of the double-blind phase, and therefore no subjects entered the OLE period. After all subjects have terminated the study, outstanding data queries have been resolved or adjudicated as unresolvable, and the data have been cleaned and finalized, the study blind will be broken and then the final analysis of the data will be performed.

3. GENERAL CONSIDERATIONS FOR DATA ANALYSES

3.1. Analysis Sets

Analysis sets define which subjects are included in an analysis.

The assignment of subjects to analysis sets will be done before database lock and the study blind is broken for analysis. A summary of the number and percentage of subjects in each analysis set will be provided by treatment group and in total.

3.1.1. Randomized

The randomized analysis set includes subjects who were randomized into the study.

3.1.2. Full Analysis Set

The “full analysis set (FAS)” identifies the analysis set that is both relevant for analysis of efficacy data from this study and as close as possible to the intention-to-treat (ITT) principle per International Conference on Harmonisation (ICH) E9 guidance. The full analysis set (FAS) is defined as all randomized subjects who received at least one dose of study drug. This will be the primary analysis set for evaluation of efficacy. For FAS, consistent with ITT, subjects will be categorized according to the assigned treatment.

3.1.3. Safety Analysis Set

The primary analysis set for safety analyses is defined as all randomized subjects who receive at least one dose of study drug. Subjects will be grouped according to the treatment received.

3.1.4. Pharmacokinetic Analysis Set

The primary analysis set for the PK analyses is defined as all randomized subjects who received at least one dose of active study drug and have any post-baseline plasma concentrations.

3.1.5. Biomarker Analysis Set

The primary analysis set for the biomarker (NT-proBNP, hsTnT) analyses is defined as all randomized subjects who received at least one dose of study drug and who have an NT-proBNP or hsTnT measurement both prior to study drug administration and after study drug administration. For the biomarker analysis set, subjects will be grouped based on the treatment received.

3.2. Subject Groups

Subjects will be grouped for analyses according to randomized treatment for efficacy analysis using FAS, where appropriate. Subjects will be grouped for analyses according to treatment received for efficacy analysis using biomarker analysis set, where appropriate. Subjects will be grouped according to actual treatment received for safety analysis using safety analysis set. The actual treatment received will differ from the randomized treatment only when the subject’s actual treatment differs from randomized treatment for the entire treatment duration.

Treatment groups are Eleclazine 30/3/6 mg and Placebo.

3.3. Strata and Covariates

Sex and age will be used as covariates in analyses of efficacy data. Age will be included in the model as a continuous covariate for analysis of continuous response variable and as a dichotomized (≥ 50 years and < 50 years) covariate for analysis of categorical or ordinal response if applicable. Strata will be included in the analyses if at least 10 subjects per treatment group are in each stratum.

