8.5.1. Primary Analysis

The change in Peak VO₂ from baseline (Screening) to Week 24 for the GS-6615 treatment group will be compared to that of the placebo treatment group using ANCOVA including terms for baseline Peak VO₂, sex, and age in the model.

Missing values will be imputed by methods to be specified in the statistical analysis plan.

A MMRM analysis will also be performed without any data imputation.

The null hypothesis is that there is no difference between the mean change in Peak VO₂ between the GS-6615 treatment group and the placebo treatment group.

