6.3. Analysis of the Primary Efficacy Endpoint

Peak VO₂ at baseline, Week 24, and change from baseline at Week 24 will be summarized by treatment group (eleclazine or placebo) for the FAS with the following descriptive statistics: sample size, mean, standard deviation, median, minimum, maximum, Q1 and Q3. The change in Peak VO₂ from baseline to Week 24 for the eleclazine treatment group will be compared to that of the placebo treatment group using analysis of covariance (ANCOVA) including terms for baseline Peak VO₂, sex, and age (continuous). This analysis will be performed on the FAS. Missing data will not be imputed.

The assumption of normality for the ANCOVA analyses will be assessed with the Shapiro-Wilk statistic and residuals will be visually examined for heterogeneity via scatter plots. If the normality assumption is violated, treatment differences will be assessed using an ANCOVA model on the rank-transformed change from baseline values.

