6.7. Summary of Efficacy Analyses

The analyses of the efficacy endpoints are summarized in the following table:

Table 6-1. Summary of Efficacy Analyses

Endpoint Description	Analysis Set	Analysis Method
Primary: Δ Peak VO ₂ at Week 24	FAS	ANCOVA
1 st Secondary: Δ MLHFQ at Week 24	FAS	ANCOVA
2 nd Secondary: Δ treadmill exercise time at Week 24	FAS	ANCOVA
3 rd Secondary: Peak VO ₂ at Week 12	FAS	ANCOVA
4 th Secondary: Δ MLHFQ at Week 12	FAS	ANCOVA
5 th Secondary: Δ treadmill exercise time at Week 12	FAS	ANCOVA
Exploratory Endpoints		
PPD		
		
		
		

Δ is the change from baseline.
 The ANCOVA model will include terms for age, sex, baseline value, and treatment.

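### SAP 3.3 makes stratum terms conditional on a count of 10 per arm, in unresolved conflict with SAP 6.3, Table 6-1 and Protocol 8.5.1, and could remove sex from the ANCOVAs (minor)

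*SAP*

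**What the plan says.** - **Randomization.** SAP 1.2: "Randomization will be stratified by sex and by age", with age cut at 50 years. This gives four sex-by-age cells, allocated 1:1.
- **Covariates, no condition.** SAP 3.3 opens with "Sex and age will be used as covariates in analyses of efficacy data" and continues "Age will be included in the model as a continuous covariate for analysis of continuous response variable".
- **Strata, with a condition.** SAP 3.3 closes with "Strata will be included in the analyses if at least 10 subjects per treatment group are in each stratum".
- **Primary model.** SAP 6.3 lists baseline Peak VO2, "sex, and age (continuous). This analysis will be performed on the FAS". SAP 6.4.2 treats the secondary endpoints similarly.
- **Table 6-1 note.** "The ANCOVA model will include terms for age, sex, baseline value, and treatment".
- **Protocol 8.5.1.** Baseline Peak VO2, "sex, and age in the model". Protocol 8.5 specifies that age is continuous.
- **Early stop.** SAP 2: "This study was terminated by the Sponsor prior to the end of the double-blind phase". Neither the number randomized nor the number with Week 24 data is given.

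SAP 6.6, which lists departures from the protocol's efficacy analyses, does not mention the count rule.

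**The concern.** Four places name sex and age as model terms outright, and one sentence makes stratum terms depend on counts. The two variables concerned are the stratification factors. Two statisticians following this SAP could therefore fit different primary models: one with sex always in, the other with sex out because a stratum is small.

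Table 6-1 gives ANCOVA as the method for the primary and all five secondary endpoints, and SAP 6.6 removes inference for exploratory endpoints. So the rule either has no remaining use or bears on exactly these models. It brings no benefit there, since sex and continuous age cost two degrees of freedom in total and nothing is estimated per cell.

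At stake is precision. Leaving out a prognostic factor that was balanced by stratified randomization makes the standard error too wide and the test conservative. The early stop matters because it may have reduced the counts on which the rule depends.

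**Working it through.** **1. The plan's own power figure.** Inputs from SAP 1.3: 90 per arm, difference 3, SD 4, two-sided alpha 0.01.

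Power = Φ(3 / (4 × √(2/90)) − 2.576) = Φ(5.031 − 2.576) = Φ(2.455) = 99.3%; the noncentral t gives 99.2%. The stated figure of more than 95% is reproduced. The point does not turn on it.

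**2. What the rule leaves undefined.**
- Whether a stratum is one of the four cells or one level of a single factor.
- Whether the count is of randomized subjects, the FAS, or those with data at the visit analysed. Only the last could give different models at Weeks 12 and 24.
- Which model applies when the rule fails.
- Whether the rule reaches the terms named in SAP 6.3.

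**3. Smallest arm that can pass.** Four cells: 4 × 10 = 40 per arm, and only if the cells are perfectly even. Factor levels: 2 × 10 = 20 per arm.

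**4. Chance that the rule fails.** Assumed, not in the documents: 25-50% women, 40-60% aged 50 or older, and the evaluable numbers per arm below. Multinomial simulation of the four cells, each split 1:1, 100,000 draws:

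| Evaluable per arm | Four-cell reading | Factor-level reading |
|---|---|---|
| 90 | under 0.1% to 68% | about 0% |
| 70 | 0.3% to 97% | up to 0.1% |
| 50 | 38% to 100% | 0% to 10% |
| 40 | essentially 100% | 0% to 46% |
| 30 | 100% | 1% to 92% |

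Hand check at 50 per arm. With 25% women, the factor-level rule needs at least 20 women among 100 subjects: P(Binomial(100, 0.25) ≤ 19) = 10.0%. With 25% women and 40% aged 50 or older, the smallest cell is expected to hold 100 × 0.25 × 0.40 = 10 subjects where 20 are needed, so failure is almost certain.

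**5. Cost if terms are dropped.** Simulated ANCOVA with stratified 1:1 assignment, 4,000 trials per setting, all models fitted to the same data. Every coefficient is assumed:
- baseline = 20 − 3·sex − 0.1·(age − 45) + error with SD 3.5
- change = difference·treatment + b_sex·sex + b_age·(age − 45)/13.6 − 0.2·(baseline − 20) + error with SD 3.8
- (b_sex, b_age) = (1, 0.7) or (2, 1.5) mL/kg/min

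Power for an assumed difference of 2 mL/kg/min at two-sided 0.05, the level in SAP 3.5, with 50 per arm:

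| Effects | Sex and age kept | Sex dropped | Both dropped |
|---|---|---|---|
| (1, 0.7) | 73.7% | 73.0% | 71.9% |
| (2, 1.5) | 72.3% | 70.1% | 65.7% |

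Using unrounded values, the loss is 0.7 to 2.2 points without sex and 1.8 to 6.6 without both. The corresponding losses are 0.1-0.7 and 0.4-3.2 points at 90 per arm, and 1.0-2.6 and 2.0-7.7 at 30.

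Across these settings, type I error is 4.4-5.2% with both terms kept and 4.1-4.7% with both dropped. The Monte Carlo standard error at 5% is √(0.05 × 0.95/4000) = 0.34 points. There is no inflation.

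**6. Cross-check.** If the dropped terms explain a share R² of residual variance, the standard error grows by 1/√(1 − R²) − 1: 2.6% at an assumed R² of 0.05 and 5.4% at 0.10.

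**The case against.** The strongest reply is that the texts can be reconciled. SAP 3.3 is headed for strata and covariates, which are two things: sex and age are fixed covariates, and the last sentence governs separate stratum terms. SAP 6.3 and Table 6-1 name the model terms specifically, and specific text would ordinarily prevail. The protocol also planned stratified Wilcoxon, CMH and logistic analyses, for which a minimum stratum count makes sense; the sentence may simply have outlived them. This stands as far as it goes. It makes the point an unresolved conflict rather than a flat contradiction, but the SAP does not state the reconciliation, and on this reading the sentence has nothing left to do.

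Three stronger readings are tempting and are not supported:

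- **That age would also be lost.** Age enters the ANCOVA as a continuous covariate, which SAP 3.3 includes without condition. Only sex is both a stratification factor and a categorical term in the model.
- **That the early stop triggers the rule.** No achieved or evaluable number is given, and on the factor-level reading the rule would rarely fail at 50 per arm or more.
- **That the comparison would be biased or its type I error inflated.** The rule is prespecified, uses counts and not outcomes, and makes the test slightly conservative.

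It is also fair that the cost depends on assumed prognostic effects. Baseline Peak VO2 stays in the model and may carry part of the influence of sex and age, as Protocol Appendix 4 predicts Peak VO2 from those two variables. At the planned difference of 3, power at 50 per arm and two-sided 0.05 is already about 96% without adjustment (normal approximation, SD 4), so less can be lost there. The setting is moreover a terminated trial with a synoptic report and nominal testing.

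**Conclusion.** The conflict is real and minor. SAP 3.3's closing sentence does not fit its own opening, SAP 6.3, the Table 6-1 note or Protocol 8.5.1, and if applied to the ANCOVAs it could remove sex. How likely that is rests on an undefined term and an unstated sample size: 38-100% on the four-cell reading against 0-10% on the factor-level reading, at an assumed 50 evaluable per arm with the assumed sex and age mix. The consequence would be a small loss of power, 0.7-2.2 points if only sex goes and 1.8-6.6 if both terms go, under the assumed prognostic effects and a difference of 2 mL/kg/min. There is no bias and no inflation of type I error.

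**What to change.** Delete the last sentence of SAP 3.3, or replace it with: *Sex and age (continuous) are included in every ANCOVA of the primary and secondary endpoints, whatever the stratum counts.* SAP 3.3, SAP 6.3, Table 6-1 and Protocol 8.5.1 then agree.

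If the sponsor wants to keep a count rule for some other analysis, name that analysis and define the stratum, the subjects counted and the fallback model.

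The change should be made before unblinding, which SAP 2 places after the data are cleaned and finalized. It costs one sentence and has no statistical downside.
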